## LIST OF ABBREVIATIONS

AE	adverse event
ALP	alkaline phosphatase
ALT	alanine aminotransferase
AST	aspartate aminotransferase
AUC	area under the curve from 0 to infinite time
AUC (0-12),ss	area under the curve from 0 to 12 hours at steady state
AUC (0-t)	area under the plasma concentration-time curve from zero to the time of the last measured concentration above the limit of quantification
bpm	beats per minute
BRV	brivaracetam
C av,ss	average plasma concentration at steady state
CDMS	clinical data management system
CI	confidence interval
CL/F	apparent total body clearance
CL ss /F	apparent total body clearance at steady state
C max	maximum plasma concentration
C max,ss	maximum plasma concentration at steady state
C min,ss	minimum plasma concentration at steady state
CPM	Clinical Project Manager
CPMP	Committee for Proprietary Medicinal Products
CRO	contract research organization
C-SSRS	Columbia Suicide Severity Rating Scale
CV	coefficient of variation
CYP	cytochrome P450
DBP	diastolic blood pressure
DEM	Data Evaluation Meeting
ECG	electrocardiogram
eCRF	electronic Case Report form
GCP	Good Clinical Practice
GMP	Good Manufacturing Practice
HRT	hormone replacement therapy

This document cannot be used to support any marketing authorization application and any extension or variations thereof.

ICH	International Council for Harmonisation
IEC	Independent Ethics Committee
IMP	investigational medicinal product
IRB	Institutional Review Board
IUD	intrauterine device
$\lambda_z$	rate constant of elimination
MedDRA®	Medical Dictionary for Regulatory Activities
MRT	mean residence time
OTC	over-the-counter
PD	pharmacodynamic(s)
PDILI	potential drug-induced liver injury
PK	pharmacokinetic(s)
PK-PPS	Pharmacokinetic Per-Protocol Set
PS	Patient Safety
PTF	peak trough fluctuation
R AUC	accumulation ratio calculated from AUC at steady state and AUC after single dose
R max	accumulation ratio calculated from C max at steady state and C max after single dose
SAE	serious adverse event
SAP	Statistical Analysis Plan
SBP	systolic blood pressure
SD	standard deviation
SFU	Safety Follow-Up
SOP	Standard Operating Procedure
SPD	Specification of Protocol Deviations
SS	Safety Set
SV2A	synaptic vesicle protein 2A
t ½	terminal elimination half-life
TEAE	treatment-emergent adverse event
t max	time to reach maximum plasma concentration
ULN	upper limit of normal
V z /F	apparent volume of distribution

This document cannot be used to support and marketing authorization application and any extensions or variations thereof.

## 1 SUMMARY

Brivaracetam (BRV) is a drug with a structure of a 2-pyrrolidinone derivative. Brivaracetam displays a high and selective interaction with synaptic vesicle protein 2A (SV2A), a protein involved in synaptic vesicle exocytosis and neurotransmitter release. This protein appears to be the primary target for BRV's pharmacological activity. Data in transgenic mice indicate that even partial SV2A deficiency may lead to increased seizure vulnerability and accelerated epileptogenesis. Brivaracetam demonstrated a potent suppression of seizure activity in a wide range of animal models of partial-onset and generalized seizures.

The clinical tolerability, pharmacokinetics (PK), and pharmacodynamics (PD) of BRV have been extensively studied up to 1400mg single dose and up to 800mg/day in repeated administration. It exhibits linear and dose-proportional PK, is rapidly and nearly completely absorbed orally, has a terminal elimination half-life ( $t_{1/2}$ ) of about 9 hours, and has plasma protein binding of <20%. Brivaracetam is extensively metabolized (>90%), primarily by non-cytochrome P450 (CYP) dependent hydrolysis of the amide group to a carboxylic acid via amidase, and secondarily through CYP2C19-mediated hydroxylation of the side chain. A third hydroxyacid metabolite is preferentially generated by CYP2C9-mediated hydroxylation of the carboxylic acid metabolite. The 3 metabolites are pharmacologically inactive.

A Phase 1, placebo-controlled, single and multiple rising dose study in healthy Japanese volunteers (N01209) has shown that the disposition of BRV was similar to that in overseas populations. Brivaracetam was well tolerated and displayed linear and dose-proportional PK. No new observations were made relative to the safety and tolerability profile of BRV. In Japanese subjects bearing 2 nonfunctional alleles of the gene coding for the CYP2C19 isoenzyme (namely, \*2/\*2, \*2/\*3 or \*3/\*3; representing 25% of the study population), formation of the inactive hydroxy metabolite was decreased 10-fold but the plasma clearance (CL/F) of BRV was only decreased by 30% (0.70mL/min/kg compared to 0.99mL/min/kg in \*1/\*1 homozygous extensive metabolizers). It was concluded that no BRV dose adaptation is necessary in Japanese subjects compared to overseas populations, and, in particular, no dose reduction is needed for subjects bearing CYP2C19 mutations.

This is a Phase 1, single site, open-label, single-dose and multiple-dose PK study of BRV tablets in healthy male and female Chinese subjects. A total of 12 subjects (6 males and 6 females) will be enrolled in the study. Subjects will be confined to the unit from Day -1 (the day prior to first administration of study drug) until Day 13 (72h after the final dose of study drug). Subjects will receive a single dose of BRV 100mg under fasting conditions in the Single-Dose Period. Blood samples will be taken predose and at specified time points postdose for the determination of the PK profile of BRV and metabolites (ucb-42145, ucb-100406-1, and ucb107092-1).

In the Multiple-Dose Period, the same subjects as in the Single-Dose Period will receive BRV 200mg/day (100mg every 12h) under fasting conditions with 200mL of water. Blood samples will be taken predose and at specified time points postdose for the determination of the PK profile of BRV and metabolites (ucb-42145, ucb-100406-1, and ucb107092-1).

Subjects will be discharged from confinement in the morning of Day 13, approximately 72h after the final administration of study drug, provided there are no medical objections.

Safety and tolerability of BRV will be monitored throughout the study by monitoring of adverse events (AEs), collecting blood and urine samples for the evaluation of safety laboratory

parameters, vital signs (systolic blood pressure [SBP], diastolic blood pressure [DBP], pulse rate, respiratory rate, and body temperature), and electrocardiograms (ECGs).

A Safety Follow-Up (SFU) Visit will be performed after the final administration of BRV. The assessments performed for the SFU will also be performed for early withdrawals.

The study objectives are to assess the PK, safety, and tolerability of BRV after a single dose and multiple doses of 100mg for 6 days in healthy adult Chinese subjects (male and female).

## 2 INTRODUCTION

A clinical development program for BRV is underway in China and will support a market authorization application/new drug application for BRV in China for the indication of adjunctive treatment in subjects 16 years and older with partial-onset seizures whether or not secondarily generalized.

The clinical tolerability, PK, and PD of BRV have been extensively studied up to 1400mg single dose and up to 800mg/day in repeated administration. It exhibits linear and dose-proportional PK, is rapidly and nearly completely absorbed orally, has a  $t_{1/2}$  of about 9h, and has plasma protein binding of <20%. Brivaracetam is extensively metabolized (>90%), primarily by hydrolysis of the amide group to a carboxylic acid supported by non-CYP dependent amidase, and secondarily through CYP2C19-mediated hydroxylation of the side chain. A third hydroxyacid metabolite is preferentially generated by CYP2C9-mediated hydroxylation of the carboxylic acid metabolite. The 3 metabolites are pharmacologically inactive.

A Phase 1, placebo-controlled, single and multiple rising dose study in healthy Japanese volunteers (N01209) has shown that the disposition of BRV was similar to that in overseas populations. Brivaracetam was well tolerated and displayed linear and dose-proportional PK. No new observations were made relative to the safety and tolerability profile of BRV. In Japanese subjects bearing 2 nonfunctional alleles of the gene coding for the CYP2C19 isoenzyme (namely, \*2/\*2, \*2/\*3 or \*3/\*3; representing 25% of the study population), formation of the inactive hydroxy metabolite was decreased 10-fold but the plasma clearance (CL/F) of BRV was only decreased by 30% (0.70mL/min/kg compared to 0.99mL/min/kg in \*1/\*1 homozygous extensive metabolizers). It was concluded that no BRV dose adaptation is necessary in Japanese subjects compared to overseas populations, and, in particular, no dose reduction is needed for subjects bearing CYP2C19 mutations.

## 3 STUDY OBJECTIVES

The study objectives are to assess the PK, safety, and tolerability of BRV after a single dose and multiple doses of 100mg for 6 days in healthy adult Chinese subjects (male and female).

## 4 STUDY VARIABLES

### 4.1 Primary pharmacokinetic variables

The primary PK variables are:

- Concentrations of BRV and 3 metabolites (ucb-42145, ucb-100406-1, and ucb107092-1) in plasma

- For the single dose:
  - $AUC_{(0-t)}$  of BRV
  - $C_{max}$  of BRV
- For the multiple dose:
  - $AUC_{(0-12),ss}$  of BRV
  - $C_{max,ss}$  of BRV

## 4.2 Secondary pharmacokinetic variables

- For the single dose:
  - $t_{max}$ ,  $t_{1/2}$ ,  $\lambda_z$ , MRT, AUC, CL/F, and  $V_z/F$  of BRV in plasma
  - $C_{max}$ ,  $t_{max}$ ,  $t_{1/2}$ ,  $\lambda_z$ ,  $AUC_{(0-t)}$ , and AUC of metabolites in plasma
- For the multiple dose:
  - $t_{max}$ ,  $t_{1/2}$ ,  $\lambda_z$ ,  $C_{min,ss}$ ,  $C_{av,ss}$ ,  $CL_{ss}/F$ , and  $V_z/F$  of BRV in plasma
  - $t_{max}$ ,  $t_{1/2}$ ,  $\lambda_z$ ,  $C_{max,ss}$ , and  $AUC_{(0-12),ss}$  of metabolites in plasma
  - PTF of BRV in steady-state
  - $R_{AUC}$  and  $R_{max}$  of BRV

## 4.3 Safety variables

### 4.3.1 Primary safety variable

- Incidence of treatment-emergent AEs (TEAEs)

### 4.3.2 Other safety variables

- Changes in vital signs (SBP, DBP, pulse rate, respiratory rate, and body temperature)
- Standard 12-lead ECGs parameters and findings
- Changes in clinical laboratory test parameters (hematology, blood chemistry, and urinalysis)

## 5 STUDY DESIGN

### 5.1 Study description

This is a Phase 1, single site, open-label, single and multiple dose PK study of BRV tablets in healthy male and female Chinese subjects. Subjects will be confined to the unit from Day -1 (the day prior to first administration of study drug) until Day 13.

A total of 12 subjects (6 males and 6 females) who sign the Informed Consent form and fulfill all inclusion and none of the exclusion criteria will be enrolled and will start the Single-Dose Period. In the Single-Dose Period, each subject will receive BRV 100mg. In the Multiple-Dose Period, the multiple-dose PK and safety of BRV 200mg/day will be evaluated in the same subjects as in the Single-Dose Period.

In the Single-Dose Period, subjects will receive a single dose of BRV under fasting conditions with 200mL water. Blood samples will be taken for the determination of the PK profile of BRV and its metabolites (ucb-42145, ucb-100406-1, and ucb107092-1) at predose, and 0.25, 0.5, 1, 1.5, 2, 3, 4, 6, 9, 12, 16, 24, 36, 48, and 72h after study drug administration.

In the Multiple-Dose Period, subjects will receive BRV 200mg/day (100mg every 12h  $\pm$ 15min). Subjects will receive BRV under fasting conditions with 200mL water. Blood samples will be taken for the determination of the PK profile of BRV and its metabolites (ucb-42145, ucb-100406-1, and ucb107092-1) predose prior to the morning dose administration on Day 5 to Day 9, and at predosing and at the following time points after the last administration of the investigational medicinal product (IMP) on Day 10: 0.25, 0.5, 1, 1.5, 2, 3, 4, 6, 9, 12, 16, 24, 36, 48, and 72h.

Subjects will be discharged from confinement in the morning of Day 13, approximately 72h after the final administration of study drug, provided there are no medical objections.

Safety and tolerability of BRV will be assessed throughout the study by monitoring of AEs, collecting blood and urine samples for the evaluation of safety laboratory parameters, measuring vital signs (SBP, DBP, pulse rate, respiratory rate, and body temperature), and ECG.

A SFU will be performed after the final administration of the IMP. The assessments performed for the SFU will also be performed for early withdrawals.

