### **5.2 Schedule of study assessments**

**Table 5–1: Schedule of study assessments**

Activity/Day	SV	Treatment Period															SFU
		Single-Dose					Multiple-Dose										
	D -28 to -2	D -1	D1		D2	D3	D4	D5	D6	D7	D8	D9	D10	D11	D12	D13	D15
			Pre	Post													
Informed consent	X																
Clinic admission		X															
Inclusion/exclusion criteria	X	X															
Demographic data	X																
Medical history	X																
Physical examination	X	X															X
Columbia-Suicide Severity Rating Scale	X	X															X
Vital signs	X		X a	X a			X a			X b			X b			X b	X
12-lead ECG	X	X c		X a			X a			X b			X b			X b	X
Safety laboratory assessments d	X		X			X									X		
Serology e	X																
Drug/alcohol test f	X	X															
Pregnancy test (serum) g	X																
Pregnancy test (urine) g		X				X										X	
IMP administration				X				X h	X i								
PK blood sampling			X	X a	X a	X a	X a	X i	X j	X j							

Adverse event/ concomitant medication/medical procedure	←														
Discharge	X														

AE=adverse event; BRV=brivaracetam; D=day; ECG=electrocardiogram; HIV=human immunodeficiency virus; IMP=investigational medicinal product; PK=pharmacokinetics; Pre=predose; Post=postdose; SFU=Safety Follow-Up; SV=Screening Visit

a See [Table 5-2](#) for the schedule for vital signs, ECGs, and PK sampling in the Single-Dose Period.

b See [Table 5-3](#) for the schedule for vital signs and ECGs in the Multiple-Dose Period.

c Three ECGs to be performed at 15min ( $\pm$ 5min) intervals within 24h prior to BRV dosing on Day 1 to provide a representative baseline.

d Hematology including coagulation parameters, clinical chemistry, and urinalysis

e Hepatitis B surface antigen, Hepatitis C virus antibody, HIV antibody, and syphilis

f Urine drug screen and alcohol breath test

g For females of childbearing potential only

h From Day 5 to Day 9, study drug will be administered in the morning and evening with an interval of 12h ( $\pm$ 15min).

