### **6.3.1 Potential drug-induced liver injury IMP discontinuation criteria**

Subjects with potential drug-induced liver injury (PDILI) must be assessed to determine if IMP must be discontinued. In addition, all concomitant medications and herbal supplements that are not medically necessary should also be discontinued.

The PDILI criterion below requires immediate discontinuation of IMP:

- Subjects with ALT or AST  $\geq 3 \times$  ULN

Evaluation of PDILI must be initiated as described in [Section 10.2.1](#). If subjects are unable to comply with the applicable monitoring schedule, IMP must be discontinued immediately.

Investigators should attempt to obtain information on subjects in the case of IMP discontinuation to complete the final evaluation. Subjects with PDILI should not be withdrawn from the study until investigation and monitoring are complete. All results of these evaluations and observations, as well as the reason(s) for IMP discontinuation and subject withdrawal (if applicable), must be recorded in the source documents. The eCRF must document the primary reason for IMP discontinuation.

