## **8.2 Day -1**

The Treatment Period consists of 14 in-house days. Subjects will stay in-house from Day -1 (day before first dosing) to Day 13. During this time, they will remain under close medical surveillance. Throughout the study, subjects will be monitored for AEs, concomitant medication, and medical procedures.

- Check subject into the clinic
- Check subject eligibility
- Perform physical examination
- Assess C-SSRS
- Perform alcohol breath test and urine drug screen
- Perform urine dipstick pregnancy test for females of childbearing potential only
- Record concomitant medication and medical procedures
- Record AEs
- Perform 12-lead ECG (3 ECGs will be performed at 15min [ $\pm 5$ min] intervals within 24h before dosing of BRV on Day 1)

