#### **8.5 Day 3**

- Obtain blood samples for safety laboratory assessments
- Perform urine dipstick pregnancy test for females of childbearing potential only
- Obtain blood sample for plasma PK at 48h postdose
- Record concomitant medication and medical procedures
- Record AEs

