## **8.16 Safety Follow-Up Visit**

The subject will return to the clinic 2 days later (Day 15) for the SFU Visit. The following procedures will be performed:

- Perform physical examination
- Assess C-SSRS
- Obtain vital signs
- Perform 12-lead ECG
- Record concomitant medication and medical procedures
- Record AEs

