### 10.2.1 Evaluation of PDILI

The PDILI IMP discontinuation criteria for this study are provided in Section 6.3.1, with the accompanying required follow-up investigation and monitoring detailed below. All PDILI events must be reported as an AE and reported to the study site and Sponsor within 24 hours of learning of their occurrence. Any PDILI event that meets the criterion for potential Hy's Law must be reported as an AE of special interest (see Section 10.1.1.3), and, if applicable, also reported as an SAE (see Section 10.1.1.2).

Evaluation of PDILI consists of the diagnostic testing and continued monitoring included in Table 10–2 (specific tests dependent on laboratory results and corresponding symptoms) and consultation with a local hepatologist (if applicable; discussed in Section 10.2.1.1). The local

---

hepatologist is the expert usually consulted by the treating physician for assessment and management of potential hepatic disease. This would usually be a hepatologist, but may be a gastroenterologist. Additional investigation and monitoring may be required and adapted based on the diagnosis after the cause of the liver injury/abnormality is confirmed (details in Section 10.2.1.3).

The results of all monitoring, including laboratory testing and other testing, should be made available to the study site and Sponsor.

All initial tests resulting in abnormal hepatic laboratory values need to be repeated, but appropriate medical action must not be delayed waiting for the repeat result.

When IMP is discontinued, all concomitant medications and herbal supplements that are not medically necessary should also be discontinued. In these cases, the Investigator should also consider dose reduction for medically necessary concomitant medication and consider changing any medically required concomitant medication known to be hepatotoxic to a suitable alternative.

The table below summarizes the approach to investigate PDILI.

REDACTED COPY

This document cannot be used to support any marketing authorization application and any reference thereto.

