#### **6.1.7        Compliance**

A study participant is considered compliant with treatment if the participant takes the study IMP at all of 12 scheduled time points. Participants who do not take all 12 doses are to be considered non-compliant to treatment and are to be discussed at the DEM. A data listing for treatment compliance is not provided.

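### A subject withdrawn after a dose on Days 5 to 10 leaves with no required safety laboratory sample after that dose

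*Protocol*

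**What the plan says.** **Early withdrawal.** Protocol 5.1 gives one rule: "The assessments performed for the SFU will also be performed for early withdrawals". Protocol 1 and SAP 1.2 repeat it. Protocol 6.3 (withdrawal criteria) adds no laboratory test.

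**Content of the SFU.** Protocol 8.16 begins: "The subject will return to the clinic 2 days later (Day 15) for the SFU Visit". It then lists physical examination, C-SSRS, vital signs, 12-lead ECG, medication and procedures, and AEs. It names no laboratory sample.

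**Safety laboratory schedule.** Table 5–1 footnote d defines the panel: "Hematology including coagulation parameters, clinical chemistry, and urinalysis". Before multiple dosing, the last required sample is on Day 3 (Protocol 8.5: "Obtain blood samples for safety laboratory assessments"). Protocol 8.6 to 8.12, covering Days 4 to 10, schedule none. The next is on Day 11 (8.13). SAP 5.6.3.1 gives Screening, Day 1 predose, Day 3 and Day 11.

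**Dosing.** One dose is given on Day 1, two a day on Days 5 to 9, and one on the morning of Day 10. SAP 6.1.7 confirms the total: "A study participant is considered compliant with treatment if the participant takes the study IMP at all of 12 scheduled time points".

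**The concern.** An SFU without laboratory tests is reasonable for completers, because they have already had the Day 11 sample. Early withdrawals are given the completers' SFU list without having had that sample.

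Of the three groups of variables in Protocol 4.3.2, vital signs and ECG are measured on Days 7 and 10 (Table 5–3) and again at the SFU. Laboratory tests have neither. If a subject stops during twice-daily dosing, no required test looks for a laboratory change without symptoms.

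What is at stake is mainly that volunteer's own safety check. A smaller matter is that the subject stays in the Safety Set without a laboratory value after multiple dosing, although laboratory change is a listed safety variable.

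**Working it through.** No figure in the plan is in dispute. The check is a reading of the schedule and a count of doses.

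**1. Dose count**
- Multiple doses: 5 days × 2 + 1 = 11.
- With the Day 1 dose: 11 + 1 = 12, which matches SAP 6.1.7.
- So 11 of the 12 doses fall between the Day 3 and Day 11 samples, an interval of 11 − 3 = 8 days.

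**2. Exposure and age of the last required sample, by day of withdrawal**

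| Withdrawn at the end of | Multiple doses taken | Cumulative mg (× 100) | Age of Day 3 sample (days) |
|---|---|---|---|
| Day 5 | 2 | 200 | 5 − 3 = 2 |
| Day 6 | 4 | 400 | 3 |
| Day 7 | 6 | 600 | 4 |
| Day 8 | 8 | 800 | 5 |
| Day 9 | 10 | 1000 | 6 |
| Day 10 | 11 | 1100 | 10 − 3 = 7 |

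The smallest case is withdrawal after the Day 5 morning dose: 1 dose, 100mg. A subject withdrawn on Day 5 before that dose has taken no multiple dose and is outside the point.

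**3. Required laboratory values after a multiple dose, for a subject withdrawn on Days 5 to 10**
- From the visit schedule (8.7 to 8.12): 0.
- From the early-withdrawal set, which is the SFU list (8.16): 0.
- From the withdrawal criteria (6.3): 0.
- Total: 0. The last required sample is Day 3, which follows the single dose only.

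**4. Do other provisions fill the gap?**
- *Liver-injury rules.* Protocol 6.3.1 acts on ALT or AST ≥3×ULN, and keeps such subjects in the study: "Subjects with PDILI should not be withdrawn from the study until investigation and monitoring are complete". Protocol 10.2.1 also starts from a result already in hand: "All initial tests resulting in abnormal hepatic laboratory values need to be repeated". With no scheduled sample between Day 3 and Day 11, a rise without symptoms need not produce such a result.
- *AE follow-up (10.1.3).* It needs a known AE.
- *Pregnancy (10.1.4).* It names an early discontinuation visit but gives it no laboratory content.
- *Unscheduled tests.* The investigator may order them; nothing requires them.

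**5. Does the answer depend on the later laboratory days?** Protocol 8.15 also lists a Day 13 sample, which SAP 5.6.3.1 does not. Neither version places a sample on Days 5 to 10 or at the SFU, so it does not matter here. The SFU column of Table 5–1 agrees as far as its layout can be read, but the point rests on 8.16.

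**6. Size in the study.** One such withdrawal would be 1/12 = 8.3% of the planned subjects. With no withdrawals there is no effect.

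**The case against.** The case for leaving the plan alone has four parts, and much of it stands.

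- **Low expected yield.** Subjects are healthy, those with ALT, AST or ALP above ULN are excluded (6.2, criterion 18a), and they are under medical surveillance in the unit. Protocol 5.3 reports experience up to 1400mg as a single dose and 800mg/day repeated. The largest cumulative exposure here is 1100mg over six days, and 200mg/day is a quarter of 800mg/day. This lowers the chance that an exit sample finds anything, but it does not replace the sample.
- **Replacement.** Dropouts for non-safety reasons are replaced by a subject of the same gender (Protocol 12.6 and 12.8; SAP 6.1.5.1 makes this optional). At dataset level this partly offsets the missing value. It does nothing for the subject who left.
- **Safety withdrawals.** A subject who leaves because of an AE has a known problem, and 10.1.3 requires follow-up. The main remaining case is a subject with no known abnormality who leaves for another reason.
- **The 8-day interval is not caused by the withdrawal rule.** Completers also take all 11 multiple doses before their next sample. Only the missing sample at exit is specific to withdrawals.

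Three stronger readings are tempting, and the documents do not support them. A reader might infer that a withdrawn subject has no laboratory protection at all; unscheduled tests, the liver-injury work-up and AE follow-up remain available. A reader might infer that the SFU needs laboratory tests for everyone; completers already have the Day 11 sample. A reader might also infer that the whole SFU set should be done before a withdrawn subject leaves. The plan sets no time for early withdrawals, and the SFU is a return visit two days after discharge. Moving it forward could lose later safety observation.

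**Conclusion.** The gap is real and follows directly from the text: a subject withdrawn after a multiple dose on Days 5 to 10 has no required safety laboratory value after that dose. It is a minor point. It depends on a withdrawal, the number of which cannot be known in advance; it concerns mainly one subject's safety check; and it alters no primary PK or TEAE result. It is worth correcting because the panel is already defined and routine.

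The conclusion assumes that 8.16 is the complete SFU list and that no laboratory test is required elsewhere for early withdrawals. I found none.

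**What to change.** Leave the early-withdrawal sentence and the SFU timing as they are. Add to Protocol 5.1, 8.16 and Table 5–1, with matching text in Protocol 1 and SAP 1.2:

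> In addition, a subject withdrawn after a dose and before the Day 11 sample will have the safety laboratory panel of Table 5–1, footnote d, taken at withdrawal: before leaving the unit where possible, otherwise at the early-withdrawal SFU assessment, if the subject agrees.

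In SAP 5.6.3.1, list the value as 'Early Withdrawal' with change from Baseline and reference-range flags. The Day 3 and Day 11 summaries and shift tables do not change.

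The sample is easy to take because subjects are confined (Protocol 8.2: "Subjects will stay in-house from Day -1 (day before first dosing) to Day 13"). The wording also reaches a subject withdrawn after the single dose, at the same small cost.

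The cost is one routine blood and urine sample per such subject, one listing label, and a small amendment with the approvals in Protocol 13.5. A subject who withdraws consent may decline. A sample at exit may fall only hours after the last dose, whereas completers are sampled the day after theirs, so it should be listed under its own label and not merged with Day 11. Completers have nothing extra.
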